### 4.3. Study Day and Analysis Visit

The *study day* describes the relative day of an observation starting with the reference date designated as Study Day 1. In this study, the treatment start date is the reference date. Thus, the study day will be calculated as:

- For a pre-baseline date, Study Day = Date Treatment Start Date
- For a post-baseline date, Study Day = Date Treatment Start Date + 1

# 4.4. Analysis Visit and Analysis Window

*Analysis visit* is a timing variable to be used for analyses involving visits. For each analysis visit, an *analysis window* is set up to determine the analysis visit to which a measurement should be mapped (Table 4). The analysis visit of a measurement will be determined based on the study day of the measurement and specified analysis windows and is not necessarily the same as the

study visit at which the measurement was collected. For example, an out-of-window measurement collected at the Day 7 study visit will be mapped to the Day 14 analysis visit, if the study day of the measurement falls into the analysis window of Day 14.

The following *analysis windows* will be applied to minimize the amount of missing data for analysis purposes:

		Analysis Window				
Analysis Visit (Target Study Day)	Protocol Visit Window			Patient Global Rating of Treatment	Blood Chemistry, Hematology, Urinalysis	Other Parameters
Baseline (Day 1)	[1, 1]			NA*	[-,1]	[-,1]
Day 7 (Day 7)	[5, 9]	-		NA*	NA*	[2, 11]
Day 14 (Day 14)	[12, 16]	-		NA *	$\mathrm{NA}^*$	[12, 23]
Month 1 (Day 30)	[27, 33]	-		NA*	[2, 49]	[24, 49]
Month 2 (Day 60)	[57, 63]			[2, -]	[50, -]	[50, day of Month 2 Visit]
Month 3 (Day 90)	[87, - ]			NA*	NA*	[day of Month 2 Visit + 1, - ]

Table 4:Analysis Visit and Analysis Window

\*Not collected at this visit.

If there are two or more visits that fall into the same analysis window, then the visit closest to the target assessment day will be selected for that visit window. In the case that two visits are equidistant to the target assessment day, i.e., one is before and one is after the target assessment day, the latter will be selected for that visit.

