8.1.8. Unscheduled Visits

If subject requires an unscheduled visit, procedures and assessments will be performed as needed.

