8.2.2. Clinical Safety Laboratory Assessments

• See Section 10.2 for the list of clinical laboratory tests to be performed and to the SoA for the timing and frequency.

- The investigator must review the laboratory report, document this review, and record any clinically relevant changes occurring during the study in the AE section of the CRF. The laboratory reports must be filed with the source documents. Clinically significant abnormal laboratory findings are those which are not associated with the underlying disease, unless judged by the investigator to be more severe than expected for the participant's condition.
- All laboratory tests with values considered clinically significantly abnormal during participation in the study or within 1 month after the last dose of study intervention should be repeated until the values return to normal or baseline or are no longer considered clinically significant by the investigator or medical monitor.
 - If such values do not return to normal/baseline within a period of time judged reasonable by the investigator, the etiology should be identified, and the sponsor notified.
 - All protocol-required laboratory assessments, as defined in Section 10.2, must be conducted in accordance with the laboratory manual and the SoA.
 - If laboratory values from non-protocol specified laboratory assessments performed at the institution's local laboratory require a change in participant management or are considered clinically significant by the investigator (*e.g.*, SAE or AE or dose modification), then the results must be recorded in the CRF.

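### The SAP's nearest-to-target rule lets an unscheduled repeat replace the scheduled laboratory value in the by-visit summaries and, at Month 2, lets an off-drug sample stand as the Month 2 result

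*SAP*

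**What the plan says.** SAP 4.4 assigns results to visits by date: "The analysis visit of a measurement will be determined based on the study day of the measurement and specified analysis windows". If two or more visits share a window, "the visit closest to the target assessment day will be selected for that visit window". If they are equally distant, "the latter will be selected for that visit". The section does not rank scheduled above unscheduled samples and does not exclude repeats.

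In SAP Table 4 the laboratory windows (chemistry, hematology, urinalysis) are Days 2 to 49 for Month 1, target Day 30, and Day 50 onward without limit for Month 2, target Day 60. For the remaining parameters the Month 2 window is "50, day of Month 2 Visit", with a Month 3 window after it.

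The assessment schedule (SAP Table 2) has post-dose laboratory samples only at Month 1 and Month 2. Protocol 8.2.2 says that clinically significantly abnormal values "should be repeated until the values return to normal or baseline or are no longer considered clinically significant". This covers values found during participation or "within 1 month after the last dose of study intervention". Protocol 8.1.8 allows the extra visits: "If subject requires an unscheduled visit, procedures and assessments will be performed as needed". SAP 3.1 has dosing continue through Visit 6 (Month 2).

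Laboratory tests are a safety endpoint (SAP 2.2.3). Protocol 9.4.6 and SAP Section 5 call for descriptive summaries, but the SAP's contents list no laboratory section under Section 9.

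**The concern.** A second laboratory sample inside a window will often exist because the first one was abnormal, and repeats continue until the abnormality has resolved or is no longer judged significant. A rule that chooses between the two on date alone can then put the later value, which is likely to be closer to normal, into the by-visit table in place of the scheduled on-treatment value.

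At Month 2 there is a further problem of labelling. Dosing ends at Visit 6 and no Month 3 laboratory window exists, so any sample drawn after Visit 6 can only map to Month 2. The table would then show an off-drug result under an on-treatment heading.

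What is at stake is the descriptive laboratory summary by visit and the change from baseline, in arms of about 30, 30 and 15 subjects. SAP Section 5 includes the minimum and maximum among its statistics, and with arms this small a single replaced value can alter them.

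**Working it through.** **Inputs.** Target days T = 30 and T = 60; visit windows T ± 3, that is Days 27–33 and 57–63; laboratory analysis windows, nearest-day rule and tie rule, all from SAP 4.4. End of dosing at Visit 6, from SAP 3.1. The plan states no figure of its own on this point, so there is none to reproduce.

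**Condition for replacement.** Let the scheduled sample fall on day d and the repeat k days later, both in the same window. The repeat is chosen when |d + k − T| ≤ |d − T|, equality counting because ties go to the later visit. For d < T this gives k ≤ 2 × (T − d). For d ≥ T no later repeat can be chosen, because it is always further from the target.

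**In-window visits.**

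| Scheduled day | Longest replacing lag | Month 1: replaced by a repeat on | Month 2: replaced by a repeat on |
|---|---|---|---|
| T − 3 (27 or 57) | 2 × 3 = 6 days | Days 28–33 | Days 58–63 |
| T − 2 (28 or 58) | 2 × 2 = 4 days | Days 29–32 | Days 59–62 |
| T − 1 (29 or 59) | 2 × 1 = 2 days | Days 30–31 | Days 60–61 |
| T to T + 3 | none | never | never |

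So 3 of the 7 in-window days are exposed, with 6 + 4 + 2 = 12 replacing combinations of day and lag at each visit. At Month 2 each of these repeats falls 1 to 6 days after Visit 6, hence off drug. At Month 1 the subject is still in the treatment period, so displacement arises there but the off-drug label does not.

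**Early or missing Month 2 sample.** For d = 50, k ≤ 2 × (60 − 50) = 20, so a repeat up to Day 70 replaces it. Day 50 is 7 days before the protocol window opens. If the Month 2 sample is missing, any later sample becomes the Month 2 value; one on Day 90 would be about 30 days after a Day 60 visit.

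**How often.** The documents give neither the repeat interval nor the rate of clinically significant abnormalities. Assume, for illustration, that each of the 7 in-window days is equally likely for the scheduled sample and that each lag up to a maximum is equally likely for the repeat:

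| Longest lag | Replacing pairs / all pairs | Share |
|---|---|---|
| 3 days | 8 / (7 × 3) = 8/21 | 38% |
| 7 days | 12 / (7 × 7) = 12/49 | 24% |
| 14 days | 12 / (7 × 14) = 12/98 | 12% |

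These are shares of scheduled–repeat pairs, not of subjects. They apply only where a repeat was taken.

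**The case against.** The strongest reply is that the values concerned are not lost. Protocol 8.2.2 has clinically relevant laboratory changes recorded as adverse events, SAP 9.2 tabulates adverse events, and SAP Section 5 lists individual data. This stands, and it limits the point to the by-visit tables. A reader might infer that on-treatment abnormalities disappear from the safety record, or that one arm is favoured. The documents do not support the first, and the second would need abnormality rates that differ by arm, which are not given.

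A reader might also infer that only abnormal values produce a competing sample. Protocol 10.2 allows additional tests whenever the investigator thinks them necessary or local regulations require them. The dependence on the result is therefore indirect and partial, though Protocol 8.2.2 makes abnormal values a mandated source of repeats.

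The contrast with the capped window for other parameters is tempting as evidence of an error, but it is not. Those measures are taken again at Month 3, so their Month 2 window has to end somewhere. Laboratory tests have no Month 3 collection, and the Patient Global Rating window is likewise open-ended. The stated aim of the windows is to reduce missing data.

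Two further limits stand. The selection rule speaks of visits, and the SAP does not say whether a repeat draw counts as one. Also, a repeat needs a result, a review and a recall before it can be drawn, so lags of 2 or 4 days may be hard to meet; the documents give no turnaround time.

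None of this answers the main point. Listings and adverse event tables do not correct a by-visit table, and reducing missing data does not require an existing scheduled value to give way to a repeat.

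**Conclusion.** The point holds as a defect in the selection rule. As written, SAP 4.4 permits a repeat to replace the scheduled laboratory value on 3 of 7 in-window days at each of Month 1 and Month 2. At Month 2 the replacing sample is off drug, by at most 6 days for an in-window original and for longer if the scheduled sample was early or missing.

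This assumes that repeats are recorded as unscheduled visits and enter the same data as scheduled samples, which nothing in the SAP excludes. It also relies on Protocol 9.4.6 and SAP Section 5 for the existence of a by-visit laboratory summary, since SAP Section 9 does not specify one and gives no worst-value or shift summary that would offset the rule.

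The consequence is modest: descriptive summaries and changes from baseline only, with no testing of safety data and no effect on the primary endpoint. It is worth correcting because the remedy is a few lines of SAP text.

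**What to change.** In SAP 4.4, for laboratory parameters:

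- Use the sample from the scheduled Month 1 or Month 2 collection whenever it exists, even if it was drawn shortly after the visit day. Use an unscheduled sample only when the scheduled one is missing. This reduces the 12 replacing combinations to 0 at both visits.
- Do not label unscheduled samples taken after the treatment end date as on-treatment Month 2 values. List them, or report them separately as post-treatment.
- Optionally, add a summary of the worst on-treatment value, or a shift table, using all scheduled and unscheduled samples.

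A hard cap of the Month 2 window at the day of the Month 2 visit is not advised. Protocol 8.1.1 and 8.1.5 tell sites to instruct the subject to complete the laboratory collection, which leaves room for a draw on another day. If the same applies at Visit 6, a cap could discard a genuine Month 2 sample. It would also be undefined if Visit 6 is missed, and it would leave Month 1 as it is.

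The cost is slightly more programming, possibly a few more missing Month 2 values, and summaries that may look slightly less favourable. No new data are needed.

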# 4.5. Extent of Exposure

The *extent of exposure* to study medication will be assessed by duration of treatment exposure, derived as:

Duration of treatment exposure = Treatment end date - Treatment start date + 1

## 5. GENERAL CONSIDERATIONS

All measures will be summarized descriptively. Continuous variables will be summarized using descriptive statistics such as number of observations (n), mean, standard deviation, standard error, median, minimum, and maximum. Categorical variables will be tabulated using frequency (n) and percent (%).

Unless otherwise specified, the following conventions will be followed in reporting the decimal places.

Reporting Statistics	Decimal places
Range (Low Value, High Value)	Recorded Decimal Places
Mean, Median	Recorded value + 1 Decimal Places
Confidence Interval, Standard Deviation, Standard Error	Recorded value + 2 Decimal Places
p-Value	4 Decimal Places (ex. 0.0021)

The statistical testing will be conducted at a significance level of 0.10 (two-sided) and the 90% confidence interval will be shown, unless specified otherwise. No statistical testing will be conducted for safety measures.

All data manipulations, descriptive summaries, and statistical hypothesis testing will be performed using Statistical Analysis System (SAS) Version 9.4 or later. Individual data, including relevant derived variables, will be listed.

Additional analyses not specified in this SAP may be conducted if deemed necessary and will be documented in the CSR.

### 5.1. Adjustments for Covariates

Details in covariates to be included in the statistical model for each individual statistical analysis are provided Section 8.

# 5.2. Handling of Missing Data

#### 5.2.1. Efficacy Measures

The primary analysis of DCNVA will be based on observed cases; hence, missing data will not be imputed. As a sensitive analysis of the primary efficacy endpoint, an analysis using mixed-effect model for repeated measures (MMRM) will be performed. The MMRM model will be applied using observed cases and no imputation will be needed.

For continuous secondary endpoints where MMRM-based analysis will be performed, no imputation will be necessary. For binary secondary endpoints with response status, the analysis will be based on observed cases; hence, no imputation will be performed.

#### 5.2.2. Safety Measures

Descriptive summaries of safety measures will be based on observed data only. No imputation of missing scores will be implemented.

#### 5.2.3. Dates for Medical Events and Medications

Completely or partially missing onset and resolution dates for AEs, Concomitant Medications (CM), and Medical History (MH) will be imputed in a conservative fashion as follows:

Incomplete Adverse Event Onset Date

- 1. Year imputation
  - If *year* is missing (or AE onset date is completely missing), then the onset date will not be imputed.
- 2. Month imputation
  - If *year* is not missing but *month* is missing, then:
    - If *year* = year of first study dose date, then set the *month* and *day* to the day and month of first study dose
    - Else if *year*  $\neq$  year of first study dose: set *month* to January
- 3. Day imputation
  - If *day* is missing (*month and year* not missing), then:
    - If year = year and month = month of first study dose, then set day to day of first study dose
    - Else if *year*  $\neq$  *year* and *month*  $\neq$  *month* of first study dose, then set *day* to first day of the *month* in the year

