9.4.1. General Considerations

9.4.2. Handling of Missing Values

For medical events including AEs and medical history, completely or partially missing onset and resolution dates will be imputed in a conservative fashion to be detailed in the SAP. Similar rules will be followed to impute the completely or partially missing start and end dates of nonstudy medications.

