### Incomplete CM or MH Onset Date

- 1. If year is missing (or CM/MH onset date is completely missing): do not impute
- 2. If *year* is not missing but *month* and *day* are missing: impute January 1st for missing *month* and *day*
- 3. If year and day are not missing but month is missing: impute January for missing month
- 4. If year and month are not missing but day is missing: impute 01 for missing day

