### Incomplete CM or MH Resolution Date

• Do not impute if any resolution date is missing.

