# 7.6. **Prior and Concomitant Medications**

Non-study medications will be categorized into prior medications and concomitant medications. Specifically, *prior medication* is defined as any non-study medication taken and ended prior to the study medication start date. *Concomitant medication* is defined as any non-study medication taken concurrently while receiving study medication, i.e., the period from first dose to last dose of a concomitant medication taken by a subject must overlap with the period from first dose to last dose to last dose of the study medication.

For this study, non-study medications, including prior and concomitant medications, will be coded using World Health Organization (WHO) Drug Global, Version September 2018, format B3. Each non-study medication will be classified using the Anatomical-Therapeutic-Chemical (ATC) classification system and mapped to a WHO Drug preferred drug name.

Non-study medications will be summarized for the Safety population. Subjects taking any prior medications will be tabulated by ATC level 3, level 4, and preferred drug name. A subject will be counted at most once for each prior medication, even if the subject took the same prior medication on multiple occasions. Subjects taking any concomitant medications will be tabulated similarly. In addition, prior medications and concomitant medications will also be listed, separately.

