### 8.5. Exploratory Analyses

# 9. SAFETY ANALYSES

# 9.1. Safety-Related Definitions

#### 9.1.1. Adverse Event

Under Protocol 101360002IN, an AE is defined as any *on*-study untoward medical occurrence (e.g., sign, symptom, disease, syndrome, intercurrent illness) that occurs in a study subject, regardless of the suspected cause and regardless of the timing of the study medication administration. An on-study AE can occur any time after the date of informed consent through the last study visit. An AE will be considered as *treatment-emergent* if the AE occurred on or after the treatment start date up to 8 days after treatment end date (or the last study visit). Treatment-emergent AEs (TEAEs) are a subset of on-study AEs. Both on-study and TEAEs will be collected, but only TEAEs will be tabulated.

The severity of each AE will be graded by the Clinical Investigator as Mild, Moderate, or Severe. AEs will also be rated by the Investigator as to their causality/relationship to the study drug.

Each AE will be classified into a system organ class (SOC) and coded to a preferred term (PT) using Medical Dictionary for Regulatory Activities (MedDRA), version 25.1 published in September 2022.

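### SAP 5.2.3 dates a partial AE onset to first dose without checking the resolution date, so a screening AE that had already ended can be counted as treatment-emergent

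*SAP*

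**What the plan says.** **Adverse events.** SAP 5.2.3 opens with a general statement: "Completely or partially missing onset and resolution dates for AEs, Concomitant Medications (CM), and Medical History (MH) will be imputed in a conservative fashion". The detailed AE rules follow.

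- Onset day missing: "If year = year and month = month of first study dose, then set day to day of first study dose".
- Onset month missing, year equal to the year of first dose: month and day are set "to the day and month of first study dose".
- Resolution date: not imputed, apart from an optional method if AE duration is needed.

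SAP 9.1.1 calls an AE treatment-emergent "if the AE occurred on or after the treatment start date up to 8 days after treatment end date (or the last study visit"). It tabulates only TEAEs, although AEs are recorded from consent onward. Protocol 8.3.1 describes TEAEs as events that began, or became more severe, after first dosing.

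**Medications.** Protocol 9.4.2 says "Similar rules will be followed to impute the completely or partially missing start and end dates of nonstudy medications". SAP 5.2.3 moves partial start dates to the earliest possible date (for a missing day, "impute 01 for missing" day). For stop dates it says "Do not impute if any resolution date is missing". SAP 7.6 defines a prior medication as "any non-study medication taken and ended prior to the study medication start date". A concomitant medication must overlap the dosing period. No default class is given.

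**The concern.** Dating an uncertain onset to first dose is a normal conservative convention: when the data cannot say whether an event preceded exposure, it is counted against treatment. That reasoning ends once a recorded resolution date shows that the event was over before the first drop. The SAP rule still applies then, and it produces a record that contradicts itself.

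AEs are collected from consent and screening lasts up to 15 days, so pre-dose events will be in the database. A misdated event would appear in the TEAE tables, not in the SAP 9.2 listing of non-TEAEs. In arms of about 30, 30 and 15 subjects, a single misplaced subject is visible in a percentage.

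The medication gap has a different cause. There the stop date decides the class, and the SAP declines to complete it.

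**Working it through.** The documents give no figure that depends on these rules, so there is nothing to reproduce. The check applies the rules to examples and then counts calendar days. All dates are illustrative.

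**1. AE example.** First dose 20 March 2023, onset recorded as March 2023 with no day, resolved 14 March 2023.

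- Year and month match first dose, so imputed onset = 20 March.
- 20 March is on or after the treatment start date, so the event is a TEAE under SAP 9.1.1.
- Duration = 14 − 20 + 1 = −5 days.
- With only the year of onset known, the imputed onset is again 20 March.

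**2. Share of affected records moved to first dose, day missing.** Inputs: screening of up to 15 days (protocol synopsis; SAP 3.1). Assumptions: true onset uniform over 1 to 15 days before dosing, first dose equally likely on any day of a 365-day year, and resolution on a known date before dosing.

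In a month of m days, the pairs of first-dose day and lag that stay in the same month number (0 + 1 + … + 14) + 15 × (m − 15) = 105 + 15(m − 15). That is 345 for 31 days, 330 for 30 and 300 for 28.

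- Total: 7 × 345 + 4 × 330 + 300 = 4,035.
- All pairs: 365 × 15 = 5,475.
- Share moved to first dose: 4,035 / 5,475 = **0.737**.

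Each month leaves 15m − [105 + 15(m − 15)] = 120 pairs with onset in the preceding month. For eleven months this gives 11 × 120 / 5,475 = 0.241. These records meet neither branch of the day rule, because its second branch requires both year and month to differ; that is a separate wording gap. For January, 120 / 5,475 = 0.022, correctly pre-dose.

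The same count with onset limited to the last 10 or 5 days before dosing gives 82% and 90%.

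Events already resolved may tend to have started earlier in screening, which would lower the share. At the extreme, with every onset exactly 15 days before dosing, the share is (365 − 12 × 15) / 365 = 185 / 365 = 0.51.

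**3. Month missing.** Only onsets in the previous calendar year escape: 1 − 120 / 5,475 = 0.978 for 15 days, and 98% to 99% across the three lengths.

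**4. Weight of one record.** 1/15 = 6.7% of placebo; 1/30 = 3.3% of an active arm (SAP 3.3).

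**5. Medication examples.** First dose 20 March 2023, last dose 19 May 2023.

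| Start | Recorded stop | Class under SAP 7.6 |
|---|---|---|
| 10 April 2023 | May 2023 | Concomitant, from the start date |
| 5 January 2023 | February 2023 | Prior, from the known month |
| 5 January 2023 | April 2023 | Concomitant, from the known month |
| 2022 | 2022 | Prior, from the known year |
| 5 January 2023 | March 2023 | Undetermined |
| 5 January 2023 | 2023 only | Undetermined |
| Unknown | March 2023 | Undetermined |

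The three undetermined cases started before dosing, or at an unknown time, and have possible stop dates on both sides of first dose.

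**The case against.** The best defence on AEs is that an event recorded as resolved before first dose did not occur on or after the treatment start date, so a sensible programmer would not flag it as a TEAE whatever onset was imputed. That may happen, but the SAP nowhere says that a recorded resolution overrides an imputed onset. An onset imputed to first dose meets the date test as written.

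Other points stand. The trigger is narrow: an AE within at most 15 days of screening, with a partial onset, resolved before dosing. Safety is descriptive and untested. Individual data are listed, so an onset after resolution could be noticed. The 74% is a share of records that already meet that trigger, not a rate of occurrence among all AEs.

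On medications, a reader might infer that any partial stop date prevents classification. The documents do not support that. A stop month wholly before first dose already meets the SAP 7.6 definition of prior, and a medication started during dosing is concomitant whenever it stopped. Nor is the opening sentence of SAP 5.2.3 a flat contradiction, since it introduces the detailed rules and some of those withhold imputation. The real mismatch is with protocol 9.4.2 on medication end dates. Medical history is not affected in any way that matters: SAP 7.3 tabulates it without using a stop date.

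**Conclusion.** The AE point holds. A stated rule gives a wrong result for screening AEs with a partial onset in the month (or year) of first dose and a known resolution before dosing. About 74% of such day-missing records would be moved to first dose under uniform onset over 15 days, and 98% to 99% of month-missing ones. Complete onset dates are unaffected. How many records qualify cannot be known from the documents; probably few.

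The medication point holds only for medications started before dosing, or at an unknown time, whose partial stop date spans first dose. Protocol 6.5.1 collects medications from the 90 days before screening, so the pattern is plausible, but its frequency is also unknown.

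Both are minor. They touch the TEAE and medication tables. A reader should not infer any effect on the primary efficacy analysis, which uses neither AE nor medication dates.

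**What to change.** **AEs.** Add to SAP 5.2.3: if the AE resolution date, or its latest possible value when partial, is before first dose, the imputed onset is no later than that date and the event is not treatment-emergent. Under the conditions counted above, this cuts the share made treatment-emergent from 74–90% to 0% and removes negative durations. Events whose resolution could fall on or after first dose keep the conservative treatment.

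**Medications.** Reconcile the SAP stop-date rule with protocol 9.4.2. One way is to set a partial stop date to its latest possible value, capped at study exit, and to class the medication as concomitant unless that date is before first dose. The three undetermined examples then become concomitant and the other four are unchanged. The small downside is that some medications stopped shortly before dosing will be counted as concomitant.

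**Cost.** Two sentences in the SAP and minor programming; no new data.
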